Potential risk of clinical significance	Summary of data/rationale for risk	Mitigation strategy
	Transaminases increased in 2 patients (1.1%), ALT increased in 2 patients (1.1%), Gammaglutamyltransferase increased in 2 patients (1.1%), Blood ALP increased in 1 patient (0.5%), Blood bilirubin increased in 1 patient (0.5%). The analysis of clinical laboratory data showed ALT increased Grade 3 in 3 patients (1.6%) and Grade 4 in 2 patients as well (1.1%); AST increased Grade 3 in 9 patients (4.9%) and Grade 4 in 3 patients (1.6%); ALP increased Grade 3 in 15 patients (8.2%) and blood bilirubin increased Grade 3 in 7 patients (3.8%).	
	- Loading dose: no Grade ≥3 TEAEs.	
	- Dose Escalation Q3W: ALT increased Grade 3 in 1 patient (6.7%), AST increased Grade 3 in 3 patients (20.0%), and ALP increased Grade 3 in 2 patients (13.3%).	
	In TCD15054 study: 2 patients (12.5%) reported with AST increased, 1 patient (6.3%) reported with ALT increased, 1 patient (6.3%) reported with Blood ALP increased and 1 patient (6.3%) reported with Gamma-glutamyltransferase increased.	
	The analysis of clinical laboratory data showed 1 patient (7.7%) reported with ALT increased Grade 4 (none with Grade 3), 1 patient (9.1%) reported with AST increased Grade 4. and 1 patient (14.3%) reported with ALP increased Grade 3.	
	ACT16146: 1 patient (12.5%) with serious Grade 3 TEAE of Hepatic enzyme increased.	
	EFC15858 study: 1 patient reported with serious AE of Grade 3 Transaminases increased.	
	ACT16525, ACT16432: no serious TEAEs of Hepatotoxicity reported.	
Systemic acute hypersensitivity reactions	Nonclinical: Not observed.	Premedication with histamine H1 antagonist.
(including anaphylaxis)	Clinical: ADCs are known to have the potential for hypersensitivity. In tusamitamab ravtansine development program very limited number of patients developed this profile of reactions.	If a patient has previously experienced an infusion-related reaction in a previous tusamitamab ravtansine administration, premedication will also include dexamethasone 10 mg IV for future infusions. Target infusion time is 1.5 h. In case of an infusion reaction, the flow rate can be decreased; minimum authorized flow rate is 33 mL/h. Recommended curative action: In case of infusion reaction ≥ Grade 2, tusamitamab ravtansine administration will be interrupted. The

Potential risk of clinical significance	Summary of data/rationale for risk	Mitigation strategy
		the previous infusion rate after the recovery.

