The tusamitamab ravtansine may be supplied at the site or from the PI/site/Sponsor to the participant via a Sponsor-approved courier company where allowed by local regulations and agreed upon by the participant.

After the study cut-off date for the secondary efficacy endpoints, participants with observed clinical benefit who are still receiving study treatment can continue on study treatment.

Study intervention will be administered until documented disease progression, unacceptable toxicity, new anti-cancer therapy initiation, or the participant's or Investigator's decision to stop the treatment, whichever comes first.

Noninvestigational medicinal product (NIMP): Premedication for tusamitamab ravtansine

Tusamitamab ravtansine has a potential risk of infusion-related reaction (IRR) and premedication should be used. All the drugs used as premedication will be entered to the concomitant premedication page.

Premedication with histamine H1 antagonist (diphenhydramine 50 mg or equivalent [eg, dexchlorpheniramine] given approximately 15 minutes [IV] to 1 hour [oral] before tusamitamab ravtansine administration) is required for all participants before administration of tusamitamab ravtansine. After first study intervention of SAR408701, patients should be observed for acute reactions at site up to 4 hours depending on any sign of drug-induced allergic reaction. Detailed instructions for dilution and administration of the IMP are provided in Pharmacy Manual. If a participant has experienced an IRR in a previous tusamitamab ravtansine administration, premedication will also include dexamethasone 10 mg IV for future infusions. If the participant does not experience any hypersensitivity reactions after 4 cycles, the premedication can be discontinued at the discretion of the Investigator.

Target infusion time is 1.5 hour. In case of an IRR \geq Grade 2, tusamitamab ravtansine administration will be interrupted. The infusion may be resumed at half of the previous infusion rate after the recovery. The flow rate can be decreased; minimum authorized flow rate is 33 mL/h.

For a regional or national emergency declared by a governmental agency that results in travel restrictions, confinement, or restricted site access, contingency measures are included in Appendix 9 (Section 10.9): Contingency measures for a regional or national emergency that is declared by a governmental agency.

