6.5 DOSE MODIFICATION

Dose adjustment and/or cycle delay are permitted in case of adverse reaction. In case of toxicity, cycle delays and dose modifications should be implemented according to the Appendix 6 (Section 10.6). Every effort will be made to administer the full dose regimen and maximize dose intensity.

Dose adjustments will be made according to the worst grade of adverse reaction observed within a cycle. If a participant experiences several adverse reactions and there are conflicting recommendations, the most conservative dose adjustment recommended should be followed.

Administration of the study treatment will be discontinued in the event of a TEAE that persists despite appropriate dose modifications or any other AE that, in the opinion of the Investigator, warrants discontinuation.

Dose modifications different from those stated in the protocol should only be made in consultation with the Sponsor unless required for immediate participant safety.

All changes to study treatment administration must be recorded in the electronic CRF (eCRF).

The acceptable treatment window for tusamitamab ravtansine administrations is 2 days.

One dose reduction is allowed for safety reason. Dose delay is allowed for safety management. Retreatment of patients that require more than one-month dose delay need to be justified with case by case risk benefit assessment. See Table 10 in Appendix 6 (Section 10.6) for guidance in dose modification or discontinuation. During the conduct of the study, second dose reduction may be needed, and need to be decided on a case by case basis following discussion with the sponsor.

If a dose reduction is necessary, the study intervention will be administered as follows:

Drug name	Dose	Reduced dose
Tusamitamab ravtansine	100 mg/m ² Q2W	80 mg/m² Q2W

Table 6 - Individual tusamitamab ravtansine dose reduction

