8.2.6 Guidelines for management of adverse events

Management of AEs related to tusamitamab ravtansine is summarized in Appendix 6 (Section 10.6).

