8.2.6.1 Hypersensitivity reactions

Premedication treatments provided as prophylactic treatment for hypersensitivity reactions are detailed in Section 6.1.

In case of event of hypersensitivity reactions, please refer to the recommended dose modification or discontinuation Table 10 (Section 10.6).

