10.5 APPENDIX 5: GENETICS

Use/Analysis of DNA

- Genetic variation may impact a participant's response to study intervention, susceptibility to, and severity and progression of disease. Variable response to study intervention may be due to genetic determinants that impact drug absorption, distribution, metabolism, and excretion; mechanism of action of the drug; disease etiology; and/or molecular subtype of the disease being treated. Therefore, where local regulations and IRB/IEC allow, a blood sample will be collected for DNA/RNA analysis from consenting participants.
- DNA/RNA samples will be used for research related to tusamitamab ravtansine or non-squamous NSCLC and related diseases. They may also be used to develop tests/assays including diagnostic tests related to CEACAM5 targeting drug and NSQ NSCLC. Genetic research may consist of the analysis of one or more candidate genes or the analysis of genetic markers throughout the genome (as appropriate).
- DNA/RNA samples will be analyzed for determination of tumor mutation profile on plasma cfDNA and tumor DNA/RNA. Subtractive mutation analysis will be performed with germline DNA data to identify tumor-specific somatic genetic aberrations.

- The samples may be analyzed as part of a multi-study assessment of genetic factors involved in the response to tusamitamab ravtansine or study interventions of this class to understand study disease or related conditions.
- The results of genetic analyses may be reported in the clinical study report (CSR) or in a separate study summary.
- The Sponsor will store the DNA samples in a secure storage space with adequate measures to protect confidentiality.
- The samples will be retained while research on study intervention continues but no longer than 15 years or other period as per local requirements.

10.6 APPENDIX 6: RECOMMENDED SUPPORTIVE CARE AND/OR DOSE MODIFICATION GUIDELINES FOR DRUG-RELATED ADVERSE EVENTS

Event	Symptoms severity (NCI-CTCAE v5.0)	Dose modification	Supportive care guidelines
Infusion-related reaction	Grade 1-2 eg, Grade ≤2 nausea, headache, tachycardia, hypotension, rash, shortness of breath.	Interrupt SAR408701 infusion. SAR408701 may be resumed only after participant recovery, at half the previous infusion rate ^a .	Give diphenhydramine 50 mg IV and/or dexamethasone 10 mg IV. Dexamethasone can be added as premedication for upcoming cycles for SAR408701

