	Grade 3-4 eg, symptomatic bronchospasm, urticaria lesions covering >30% BSA, hypotension, angioedema.	Interrupt SAR408701 infusion and definitively discontinue SAR408701.	Give diphenhydramine 50 mg IV and/or dexamethasone 10 mg IV and/or epinephrine and any required treatment per Investigator judgment.
Ocular toxicity: Keratopathy/keratitis ^b associated with SAR408701	Grade 1 Asymptomatic, Corneal lesions only observed on routine ocular examination and not requiring topical treatment.	Next infusion of SAR408701 at the same dose, with or without cycle delay, depending on the recommendation from the ophthalmologist (nature and extent of the lesion).	Standard ocular examination is planned as recommended by the ophthalmologist.

Table 10 - Recommended Dose Modification or Discontinuation for SAR40870

Event	Symptoms severity (NCI-CTCAE v5.0)	Dose modification	Supportive care guidelines
	Grade 2 Symptomatic, moderate decrease in visual acuity (best corrected visual acuity 20/40 and better or 3 lines or less decreased vision from known baseline)	1 st episode: SAR408701 cycle delay until resolution to Grade 1 (asymptomatic) and restart SAR408701 at the same dose. 2 nd episode: delay cycle until resolution to Grade 1 (asymptomatic) and SAR408701 dose reduction.	Standard ocular examination weekly until resolution ^{c} . Start curative treatment per ophthalmologist recommendation. After resuming study treatment, participant should be followed with standard ocular examination by every 2 cycles, even asymptomatic during next four cycles. If no recurrence, standard process with follow-up with ocular symptom is resumed. Management of study drug and follow-up process upon recurrence
	Grade 3 Symptomatic with marked decrease in visual acuity (best corrected visual acuity worse than 20/40 or more than 3 lines of decreased vision from known baseline, up to 20/200); corneal ulcer; limiting self-care ADL.	1 st episode: SAR408701 cycle delay until resolution (asymptomatic) and restart SAR408701 with dose reduction. 2 nd episode: definitive discontinuation of SAR408701.	to be discussed according to Grade of the event at recurrence, clinical benefit from study drug and recommendation from the ophthalmologist.

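### Section 6.1 lets an infusion resume at half rate after any infusion reaction of Grade 2 or higher, while Table 10 requires permanent discontinuation at Grade 3-4; and for drug-related AST/ALT rises, Table 10's Grade 1-2 row allows doses that Section 6.5.1 bars

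*Protocol*

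**What the plan says.** **Infusion-related reactions.** Section 6.1 gives the target infusion time, the flow rate and the action for a reaction. The trigger for interruption is Grade 2 or higher, and the next sentence is "The infusion may be resumed at half of the previous infusion rate after the recovery". The same section's premedication paragraph says that after an earlier reaction, of whatever grade, "premedication will also include dexamethasone 10 mg IV for future infusions". Table 1 in Section 2.3.1 uses the same trigger: "In case of infusion reaction ≥ Grade 2, tusamitamab ravtansine administration will be interrupted".

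Table 10 (Section 10.6, Appendix 6) splits by grade. At Grade 1-2 the infusion is interrupted and "SAR408701 may be resumed only after participant recovery, at half the previous infusion" rate. At Grade 3-4 the instruction is "Interrupt SAR408701 infusion and definitively discontinue SAR408701".

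Three sections lead to Appendix 6. Section 6.5 says "cycle delays and dose modifications should be implemented according to the Appendix 6"; Section 8.2.6 says "Management of AEs related to tusamitamab ravtansine is summarized in Appendix 6"; and Section 8.2.6.1, on hypersensitivity, says "please refer to the recommended dose modification or discontinuation Table 10 (Section 10.6)".

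**Hepatic enzymes.** Table 10's hepatic row for Grade 1-2 tells the site to give the drug on schedule, with no intervention. Section 6.5.1 lists criteria that must all be met on Day 1 of each later cycle. Among them are AST and ALT at or below 2.5 × ULN (5 × ULN with documented liver metastasis) and no IMP-related toxicity above Grade 1, alopecia aside, or baseline severity. Section 8.2.6.6 equates hepatic Grade 3 or higher with values above 5 × ULN.

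**The concern.** The protocol gives two answers to the same bedside question. For a Grade 3-4 infusion reaction, Section 6.1 read alone permits re-exposure once the participant recovers, whereas Table 10 ends treatment for good. Table 10's own examples at that level include symptomatic bronchospasm and angioedema. Section 6.1 is where infusion time and flow rate are set, so it is a natural place for staff to look during a reaction.

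The hepatic conflict arises on Day 1 of a later cycle. A site that works from Table 10 could dose a participant whom Section 6.5.1 makes ineligible that day.

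What is at stake is participant safety and uniform conduct across sites.

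**Working it through.** No arithmetic applies, because the plan states no figure on this point. The check sets the texts side by side.

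**Infusion-related reaction**

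| Grade | Section 6.1 | Table 10 | Result |
|---|---|---|---|
| 1 | No interruption stated | Interrupt; may resume at half rate | Differ on interruption; the intended rule is unclear |
| 2 | Interrupt; may resume at half rate | Interrupt; may resume at half rate | Agree |
| 3-4 | Interrupt; may resume at half rate | Interrupt and stop permanently | Conflict |

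At Grade 3-4 the next question is which text is intended. Sections 6.5, 8.2.6 and 8.2.6.1 all send the reader to Appendix 6 or Table 10, and none sends the reader to Section 6.1. Table 10 is therefore the intended rule. None of the three says that it overrides Section 6.1, and the resumption sentence there has no grade limit and no pointer, so the sentence stays wrong as written. In Table 1 only the Grade 2-or-higher trigger is fully legible; whether its resumption wording matches Section 6.1 has to be checked in the source.

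**Hepatic enzymes, drug-related rises**

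1. Upper end of the Table 10 Grade 1-2 row: Section 8.2.6.6 starts Grade 3 above 5 × ULN, so the row runs up to and including 5 × ULN.
2. Section 6.5.1 limit without liver metastasis: 2.5 × ULN.
3. Overlap without liver metastasis: above 2.5 and up to 5 × ULN. Table 10 doses; Section 6.5.1 bars.
4. Section 6.5.1 also bars IMP-related toxicity above Grade 1 or baseline severity. An IMP-related Grade 2 rise above baseline severity is therefore barred with or without liver metastasis, while Table 10 doses.
5. An IMP-related Grade 1 rise at or below 2.5 × ULN meets both texts, so there is no conflict.
6. Appendix 6 is headed as guidance for drug-related events. For a rise not related to the drug, Section 6.5.1 alone applies and there is no conflict.

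Table 10 writes out a delay elsewhere when it intends one. Its neutrophil Grade 2 row holds the cycle until recovery, in line with Section 6.5.1, and its hepatic Grade 3 row ties restart to recovery to Grade 1. The hepatic Grade 1-2 row has no such condition.

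**The case against.** **On infusion reactions**, the defence is that Section 6.1 only permits resumption, so a site that stops at Grade 3-4 breaches nothing. Section 8.2.6.1 names Table 10 directly, Section 6.1 itself ends treatment at unacceptable toxicity, and Section 7.1.1 requires a stop for an unacceptable AE. The dexamethasone sentence presupposes that there will be further infusions. All of this is fair, and a careful site would probably stop. But a permission to resume that another section forbids is still an error, and the cross-references reveal the intended rule without correcting the sentence.

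A reader might also infer that Section 6.1 and Table 1 are wrong at Grade 1 because Table 10 interrupts there. The documents do not settle that: Section 6.1 and Table 1 both use Grade 2 or higher.

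**On hepatic enzymes**, the defence is that Section 6.5.1 is mandatory while Table 10 is titled as recommended modifications, and that giving the drug as planned can mean subject to the retreatment criteria. The first part stands: Section 6.5.1 is the natural controlling text, and Section 7.1.3 also refers to it for reinitiation. A reader might go further and say that nothing indicates which text prevails; that is too strong given this wording. What remains is that the row is unconditional and no sentence says Section 6.5.1 prevails. The most-conservative rule in Section 6.5 is worded for a participant with several reactions, not for two sections that disagree about one.

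**Conclusion.** Both points hold. Section 6.1 is wrong as written at Grade 3-4. Table 10's hepatic Grade 1-2 row permits dosing that Section 6.5.1 bars, for drug-related AST/ALT above 2.5 and up to 5 × ULN without liver metastasis and for IMP-related Grade 2 rises above baseline severity.

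A reader might infer that every Day 1 value in the 2.5 to 5 × ULN band is in conflict. It is not, because rises unrelated to the drug fall outside Appendix 6.

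A reader might also try to size the hepatic problem from the Grade 3-4 AST counts in Table 1. Those values lie above 5 × ULN, outside the band, and do not measure it. The documents give no rate for Grade 3-4 infusion reactions or for AST/ALT in the band, so no number of affected participants can be given.

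The consequence is for participant safety and conduct only. Sample size and the interim rule do not depend on these instructions, and the primary estimand counts response regardless of treatment discontinuation.

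The conclusion assumes that Table 10 states the intended rule at Grade 3-4, as the cross-references indicate, and that the Section 8.2.6.6 threshold marks the top of hepatic Grade 2.

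**What to change.** 1. **Section 6.1, and Table 1 if its text matches:** limit half-rate resumption to Grade 2 or lower and add *Grade 3-4: definitively discontinue, see Table 10*.
2. **Section 6.1 premedication:** limit the dexamethasone sentence to participants who may be re-dosed.
3. **Grade 1 reactions:** the sponsor should choose one interruption rule and use it in Section 6.1, Table 1 and Table 10.
4. **Table 10, hepatic Grade 1-2 row:** *administer as planned if the Section 6.5.1 Day 1 criteria are met, otherwise delay*.
5. **Section 6.5:** state that Section 6.5.1 governs wherever it is stricter than Table 10.

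The cost is a text clarification by amendment or site letter, with no new visits, procedures or participants. Item 4 may delay some doses that the Table 10 row alone would allow, but Section 6.5.1 already requires those delays.

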6.2 PREPARATION, HANDLING, STORAGE, AND ACCOUNTABILITY

- 1. The Investigator or designee must confirm appropriate temperature conditions have been maintained during transit for all study intervention received and any discrepancies are reported and resolved before use of the study intervention.
- 2. Only participants enrolled in the study may receive study intervention and only authorized site staff may supply or administer study intervention. All study intervention must be stored in a secure, environmentally controlled, and monitored (manual or automated) area in accordance with the labeled storage conditions with access limited to the Investigator and authorized site staff.
- 3. The Investigator, institution, or the head of the medical institution (where applicable) is responsible for study intervention accountability, reconciliation, and record maintenance (ie, receipt, reconciliation, and final disposition records).
- 4. Partially-used study treatments will be destroyed at the study site according to the standard practices of the site after an accurate accountability has been performed and signed by the Investigator (or the pharmacist). A detailed treatment log form of the destroyed study treatments will be established with the Investigator (or the pharmacist) and countersigned by the Investigator and the Monitoring Team.
- 5. The Investigator must not destroy the unused IMP unless sanofi provides written authorization.
- 6. Further guidance and information for the final disposition of unused study interventions are provided in the pharmacy manual and/or monitoring plan.

Any quality issue noticed with the receipt or use of an IMP (deficiency in condition, appearance, pertaining documentation, labeling, expiration date, etc) must be promptly notified to the Sponsor. Some deficiencies may be recorded through a complaint procedure (see Section 8.3.8).

A potential defect in the quality of IMP may be subject to initiation of a recall procedure by the Sponsor. In this case, the Investigator will be responsible for promptly addressing any request made by the Sponsor, in order to recall the IMP and eliminate potential hazards.

Under no circumstances will the Investigator supply IMP to a third party, allow the IMP to be used other than as directed by this clinical trial protocol, or dispose of IMP in any other manner.

6.3 MEASURES TO MINIMIZE BIAS: RANDOMIZATION AND BLINDING

Not applicable as this is a single-arm, nonrandomized, open-label study; however, the specific study intervention to be taken by a participant will be assigned using an interactive response technology (IRT). The site will contact the IRT prior to the start of the study intervention

administration of each participant. The site will record the study intervention assignment on the applicable case report form.

6.4 STUDY INTERVENTION COMPLIANCE

- Methods used by the Investigator or his/her delegate to ensure that the IMP was administered.
 - The person responsible for drug dispensing is required to maintain adequate records of the IMPs. These records (eg, drug movement form) include the date the IMPs are received from the Sponsor, dispensed to the participant, and destroyed or returned to the Sponsor. The packaging batch number (IP number) and the treatment number on the vial must be recorded on the drug accountability form. The person responsible for drug administration to the participant will precisely record the date and the time of the drug administration to the participant.
- IMP compliance:
 - The Investigator records the dosing information on the appropriate page(s) of the case report form (CRF)
 - The monitor in charge of the study then checks the CRF data by comparing them with the IMP which he/she has retrieved and intervention log forms

When participants are dosed at the site, they will receive study intervention directly from the Investigator or designee, under medical supervision. The date and time of each dose administered in the clinic will be recorded in the source documents. The dose of study intervention and study participant identification will be confirmed at the time of dosing by a member of the study site staff other than the person administering the study intervention.

